## 2. SYNOPSIS

|                      |   |  |
|----------------------|---|--|
| Trial Title          | A study to determine regional lung function in patients undergoing radiotherapy using hyperpolarized xenon gas MR imaging  |  |
| Short title          | Hyperpolarized Xenon gas MR Imaging in Radiotherapy
HPX-2011-003   |  |
| Clinical Phase       | Phase II  |  |
| Trial Design         | Cohort Study  |  |
| Trial Participants   | Patients considered suitable for radiotherapy that will affect the lung.  |  |
| Planned Sample Size  | 30  |  |
| Treatment duration   | Hyperpolarized xenon gas will be administered for completion of hyperpolarized Xe-129 MRI scans. Radiotherapy as per local departmental protocols   |  |
| Follow up duration   | 9 months  |  |
| Planned Trial Period | 7 years   |  |
|                      | Objectives  | Outcome Measures/Endpoints   |
| Primary              | To demonstrate that hyperpolarized Xe-129 is sensitive to change following pulmonary radiotherapy, and thus may be developed as an objective and quantifiable method of functional lung assessment in patients undergoing radiotherapy that affects the lung            | Change in hyperpolarized Xe-129 MR imaging from baseline to other time points post radiotherapy initiation.  |
| Secondary            | 
To obtain preliminary data demonstrating if changes in hyperpolarized Xe-129 MR imaging correlate with subjective and objective responses following pulmonary radiotherapy.
 
To obtain preliminary data demonstrating if baseline hyperpolarized Xe-129 MR
 | 
Change in hyperpolarized Xe-129 MR imaging parameters from baseline to other time points post radiotherapy initiation compared to subjective and objective measures of lung function.
 
Comparison of hyperpolarized Xe-129 MR imaging and four-
 |

**Hyperpolarized Xenon gas MR Imaging in Radiotherapy**

|  |  |  |
|--|--|--|
|  | 
imaging is a more reliable clinical indicator of patient respiratory tolerance to pulmonary radiotherapy than conventional lung function testing by determining the relationship between hyperpolarized Xe-129 MR imaging indices and functional patient outcome measures (dyspnoea and radiation-induced lung toxicity assessment).
 
To use functional lung information in virtual predictive and adaptive radiotherapy treatment planning.
  | 
dimensional CT (4D-CT) at baseline.
 
Retrospective comparison of modified radiotherapy treatment planning incorporating functional lung information from hyperpolarized Xe-129 MR imaging with conventional radiotherapy treatment plans.
 |
| Investigational Medicinal Product(s)       | Hyperpolarized xenon gas   |  |
| Formulation, Dose, Route of Administration | 
The xenon gas will be hyperpolarized in the Radiology department, Churchill Hospital.
 
We will administer a maximum of 6 x 1 Litre doses of hyperpolarized xenon gas to each participant per hospital visit for Xe-129 lung MR imaging. If it is not essential to give 100% xenon for imaging, the gas may be diluted with ultrapure nitrogen. The ratio of xenon to nitrogen will vary from 10% to 100% but the volume provided to the patient will always be 1 L.
 
The route of administration is inhalation.
 |  |

**Hyperpolarized Xenon gas MR Imaging in Radiotherapy****3. ABBREVIATIONS**

|                                 |   |
|---------------------------------|---|
| ADC                             | Apparent diffusion co-efficient                     |
| AE                              | Adverse event                                       |
| AR                              | Adverse reaction                                    |
| BRC                             | Biomedical Research Centre                          |
| cm  s  | Square centimetres per second (measure of ADC)      |
| CI                              | Chief Investigator                                  |
| COPD                            | Chronic obstructive pulmonary disease               |
| CRF                             | Case Report Form                                    |
| CRT                             | Chemoradiotherapy                                   |
| CT                              | Computed tomography                                 |
| 4D-CT                           | Four-dimensional computed tomography                |
| CTCAE                           | Common terminology criteria for adverse events      |
| CTA                             | Clinical Trials Authorisation                       |
| EBRT                            | External beam radiotherapy                          |
| EPI                             | Echo Planar Imaging                                 |
| FEV 1                | Forced Expiratory Volume in one second              |
| FVC                             | Forced Vital Capacity                               |
| FiXe                            | Fraction of inhaled xenon                           |
| FXe                             | Fraction of xenon                                   |
| GCP                             | Good Clinical Practice                              |
| GP                              | General Practitioner                                |
| He                              | Helium  |
| IB                              | Investigators Brochure                              |
| IMP                             | Investigational Medicinal Product                   |
| L                               | Litre   |
| LPV                             | Lobar perfusion Value                               |
| MAC                             | Maximum Alveolar Concentration                      |
| MHRA                            | Medicines and healthcare products regulatory agency |
| MLD                             | Mean lung dose                                      |
| MR/MRI                          | Magnetic resonance imaging                          |
| NIHR                            | National Institute for Health Research              |
| NSCLC                           | Non-small cell lung cancer                          |
| PO 2                 | Partial pressure of oxygen                          |

**Hyperpolarized Xenon gas MR Imaging in Radiotherapy**

|                  |   |
|------------------|---|
| PTV              | Planning target volume  |
| PV               | Perfusion values  |
| R&D              | NHS Trust R&D Department  |
| REC              | Research Ethics Committee   |
| RILT             | Radiation induced lung toxicity   |
| RT               | Radical radiotherapy  |
| SAE              | Serious Adverse Event   |
| SaO 2 | Arterial oxygen saturation  |
| SAR              | Serious Adverse Reaction  |
| SOP              | Standard Operating Procedure  |
| SPV              | Segmental perfusion value   |
| SUSAR            | Suspected Unexpected Serious Adverse Reactions                              |
| S\V              | Alveolar surface area per unit volume of gas                                |
| TMF              | Trial Master File   |
| TSG              | Oxford Radcliffe Hospitals Trust / University of Oxford Trials Safety Group |
| VPV              | Ventilation perfusion volume  |
| VDV              | Ventilation defect volume   |
| Xe               | Xenon   |
| XTC              | Xenon Transfer Contrast   |

#### 4. BACKGROUND AND RATIONALE

Lung cancer is the second most common cancer in the UK, with approximately 39,000 new cases diagnosed each year (1). It is the most common cause of cancer death for both men and women in the UK, accounting for 22% of all cancer deaths, which equates to around 34,500 people. Survival rates for lung cancer are poor. One year survival rates in the UK for males is 27% and for females 30%, falling to less than 10% at five years (2). Prognosis for lung cancer is so poor because over two thirds of patients are diagnosed at a late stage when curative treatment is not possible. Early diagnosis and assessment of tolerance for curative treatment would make a significant difference to survival rates.

Histologically, approximately 80% of lung cancer is non-small cell lung cancer (NSCLC). The main curative treatments for NSCLC are surgery, radical radiotherapy (RT) and radical chemoradiotherapy (CRT).

##### 4.1. Radiation induced lung toxicity (RILT)

Radiation induced lung toxicity (RILT) occurs when normal lung tissue is irradiated while treating tumours. RILT presents in two phases designated radiation pneumonitis (acute) and fibrosis (late). Radiation pneumonitis generally occurs between two and seven months after RT and may present clinically with cough, dyspnoea, fever and chest pain or with radiographic changes only. Acute pneumonitis is treated with steroids but can be life-threatening even with treatment, though with early identification and treatment most patients recover. If untreated, acute pneumonitis can progress to permanent fibrosis after more than six months. RILT has been shown to increase in frequency after increased radiation dose, increased volume of the lung irradiated, some combinations of chemotherapy and RT, previous radiation and steroid withdrawal.

The risk of developing RILT can be determined by assessment of the mean lung dose (MLD) and volume of lung receiving a dose of 5-20 Gy ( $V_{5-20}$ ) over a course of radical RT (3-10). By reducing set-up variability and tumour motion due to respiration, the planning target volume (PTV) margins can be reduced, thus reducing the amount of normal lung irradiated and potentially resulting in a lower risk of RILT.

**Hyperpolarized Xenon gas MR Imaging in Radiotherapy****4.2. Functional imaging can identify lung injury**

Radiation planning using only computed tomography (CT) data has traditionally treated all regions of the lung equally. However, most gas exchange occurs in the inferior aspects of the lung and irradiation of this region is correlated with risk of RILT. By identifying functioning lung that is irradiated, ventilation and perfusion imaging may improve prediction and assessment of pulmonary toxicity following radiotherapy. Pulmonary perfusion-weighted treatment plan optimization may be useful in reducing radiation damage in patients with large perfusion defects.

External Beam RT (EBRT) planning has traditionally used anatomic imaging to aid localisation of the target structures and surrounding normal structures. The risk of RILT with radical RT is based on the assumption that lung function is spatially uniform. There is evidence, however, that the functional subunits that contribute to whole lung function are not uniformly distributed (11). This is confounded by potential variations in lung function due to tumour characteristics and patient co-morbidity. Functional imaging of the lung using SPECT  $^{99m}\text{Tc}$  labelled macroaggregate albumin provides 3D information on the distribution of pulmonary blood flow and may equate to areas of normal lung function (12). Imaging with hyperpolarized xenon gas MRI has an added advantage, as it not only provides 3D information on lung ventilation but potentially also provides information on lung perfusion. By identifying functioning lung that is irradiated, ventilation and perfusion imaging may improve prediction and assessment of pulmonary toxicity following radiotherapy.

**4.3. Current pulmonary functional imaging is limited**

Currently assessment of patients for radiotherapy involves lung function measurements to provide a clinical indicator as to whether or not the patient would tolerate treatment and maintain sufficient functioning lung post-treatment to continue with activities of daily living without significant impairment. The current gold standard for assessment of lung function is spirometry and gas transfer. Spirometry and gas transfer reflect *global* lung function but provides no information about the different regions of the lung or regarding the support 'framework' of the lung, the parenchyma. Changes in lung function as measured by spirometry do not coherently correlate with symptom severity or reflect a decline in patient health (13). This weak relationship is probably because the lung is a complex regional organ where localized disturbances of a variety of factors including gas flow (ventilation), blood flow (perfusion) and gas transfer all combine to impair respiratory function.

Some imaging techniques can detect regional lung health, however each has limitations. Computed X-ray tomography (CT) provides structural, rather than functional readout and exposes patients to both radiation and contrast. FDG-PET provides an individualized estimate of radiation response, but not pulmonary function information. Scintigraphy (SPECT) with radioactive gas, can

**Hyperpolarized Xenon gas MR Imaging in Radiotherapy**

detect regional lung function changes from irradiation. However, SPECT has low spatial resolution and exposes the patient to ionizing radiation. Both SPECT and PET also expose patients to ionizing radiation.

**4.4. Rationale for Hyperpolarized Xe-129 MR Imaging in Radiotherapy**

Hyperpolarized Xe-129 MR imaging will provide regional functional information about the lung that may be useful in predicting RILT post radiotherapy. It is feasible to co-register hyperpolarized Xe-129 MRI with RT planning scans. Incorporating information from hyperpolarized Xe-129 MR imaging into radiotherapy planning has the potential to minimise and predict RILT.

Hyperpolarized Xe-129 MR imaging offers the potential to inform the radiotherapy planning process so that parts of the lung demonstrated to function well are spared at the expense of less functional/diseased parts. This may reduce radiotherapy side effects and enable individuals who would otherwise be unsuitable for radical treatment to receive potentially curative therapy.

**4.5. Hyperpolarized noble gas MR Imaging**

The first hyperpolarized gas MR images were obtained using Xe-129 in a mouse heart lung preparation by Albert et al. (14), followed shortly by hyperpolarized He-3 images of human lungs by MacFall et al. (15). In subsequent years, hyperpolarized He-3 MR imaging became the focus of investigation due to inherent advantageous physical properties. He-3 has a larger magnetic moment than Xe-129 giving an increased signal to noise ratio. Also, until recently polarization methods were capable of achieving 30-50% polarization levels for He-3 but only 10 % for Xe-129 (16, 17). Both of these factors contributed to a stronger MR signal for He-3 compared with Xe-129. In contrast, Patz et al. has described a modified polarization method, which enables 55% polarization levels of Xe-129 to be achieved at a production rate of 5.5 litres/hour (18). These levels of polarization are comparable to those previously published for He-3, making Xe-129 an increasingly attractive agent given its large natural abundance and wide availability.

[figure not shown]
**4.6. Methods of Hyperpolarization**

In their natural form, noble gases (Xe-129 and He-3) have low magnetic moments generating a

### Hyperpolarized Xenon gas MR Imaging in Radiotherapy

weak MR signal. Compared to protons, which are abundant throughout the body, there is a limit to the amount of noble gas that can be administered into the lungs. Laser optical pumping is a technique employed to enhance the nuclear polarization of noble gases via a process called hyperpolarization. This technique was developed over 50 years ago and has been extensively applied within the field of physics research (19, 20). Hyperpolarization results in the polarization of noble gases 100, 000 times greater than the polarization of hydrogen nuclei in conventional MRI. This large net polarization gives rise to a large MR signal. In this way hyperpolarization compensates for the low physical density of noble gases introduced to the lungs permitting good visualization of the airspaces. The MR signal is generated by the hyperpolarization of He-3/Xe-129 and is completely independent of the field strength, unlike conventional MRI (21-24). It is therefore possible to perform hyperpolarized Xe-129 MR imaging in a lower field strength with the benefit of reduced susceptibility artefacts. However most studies to date have been undertaken with 1.5T systems due to availability.

Comprehensive details of hyperpolarization methods have been previously published (20, 25-29). There are two methods of laser optical pumping including alkali-metal spin exchange (30) and metastability exchange (19). Hyperpolarization of Xe-129 can only be performed by the spin exchange technique. Both methods employ circularly polarized light at different wavelengths. In brief, the spin exchange technique (*Figure 1.*) involves heating a glass cell containing He-3 or Xe-129 and rubidium metal to produce rubidium vapour. The rubidium atoms absorb circularly polarized laser light illuminating the cell, resulting in high polarization of rubidium by “optical pumping”. Collision between the polarized rubidium atoms and noble gas atoms transfers the polarization by “spin exchange”. The product is hyperpolarized He-3 or Xe-129 atoms.

*Figure 1.* from (16).

Challenges faced when imaging hyperpolarized noble gases include the following: -

1. The hyperpolarization generating the MR signal is “non-renewable”. Some polarization will be consumed during image acquisition and may only be replenished by the introduction of additional hyperpolarized gas.

**Hyperpolarized Xenon gas MR Imaging in Radiotherapy**

2. The paramagnetic properties of oxygen within the lungs leads to a loss of polarization and decay of MR signal. However, this characteristic can be utilized beneficially to measure intrapulmonary PO2.
3. He-3 is highly diffusive resulting in MR signal loss.

MR pulse sequences have been developed to account for these factors and enable regional imaging of lung structure and function down to the level of the secondary pulmonary lobule.

**4.7. Hyperpolarized Helium (He-3) MR Imaging**

To date, hyperpolarized helium (He-3) gas MRI has been the focus of ventilation imaging research. However He-3 is expensive and limited in world supply necessitating further investigation into other suitable gases, namely Xe-129. The techniques and findings from previous research with hyperpolarized He-3 MR imaging form the basis of the current study. A summary of the current literature has been therefore been included.

In normal individuals, the inhaled hyperpolarized He-3 gas is distributed homogenously throughout the lung airspaces. In contrast, localized regions deficient in hyperpolarized gas and therefore MR signal represent ventilation defects. These have been shown in a range of lung pathologies e.g. asthma, chronic obstructive pulmonary disease (COPD), cystic fibrosis (31) and bronchiolitis obliterans (32, 33). The size and extent of ventilation defects demonstrated with hyperpolarized gas MR correlate with spirometry (16, 31). Furthermore, hyperpolarized gas MRI has shown increased sensitivity in detecting ventilation abnormalities compared with spirometry and lung ventilation scintigraphy (16, 34).

“Dynamic ventilation images” may be obtained with hyperpolarized gas MRI by employing ultrafast pulse sequences (35-38). Dynamic ventilation imaging allows the distribution and severity of air trapping to be assessed directly (37, 38) and has been performed to evaluate air trapping in patients with bronchial asthma (37) and cystic fibrosis (38).

Several methods for the quantitative measurement of regional lung ventilation using hyperpolarized He-3 MRI have been suggested in experimental animal studies (39-41). In a rat model of emphysema, the ventilation abnormalities detected preceded the histological changes seen in lung alveoli (42). This study, demonstrated detectable lung functional changes before structural abnormalities and further supports hyperpolarized gas MR functional imaging for earlier diagnosis in pathological disease processes.

The diffusion coefficient of a particular gas determines the average distance its atoms move in a given period of time. The lung microstructure acts to restrict the diffusion of hyperpolarized noble gas atoms enabling the average short time diffusion coefficient, (apparent diffusion coefficient, ADC) to be measured with MRI (43). Increased ADC values have been reported with

**Hyperpolarized Xenon gas MR Imaging in Radiotherapy**

hyperpolarized He-3 MR imaging in emphysema, reflecting the increased free movement of He-3 gas atoms permitted by alveolar tissue destruction (43-46). In this way, regional ADC values can be used as a surrogate measure of alveolar airspace size. Precise correlations between hyperpolarized gas MRI ADC measurements and histological measurements of alveolar size have been reported (47-49). ADC values with hyperpolarized He-3 MR imaging have proven highly reproducible (50, 51), and been shown to correlate strongly with lung function tests (44).

Another potential application of ADC measurements is the assessment of radiation induced lung injury. Post radiation therapy, lower hyperpolarized He-3 ADC values may represent reduced alveolar volumes associated with fibrosis of the interstitium (52).

In the presence of oxygen within the lung, hyperpolarized noble gases undergo hastened loss of polarization resulting in a predicted reduced MR signal (53). This known paramagnetic effect of oxygen on He-3 gas may therefore be utilized to quantitatively measure intrapulmonary PO2 (54, 55). Reproducibility of intrapulmonary PO2 measurements has been confirmed.

#### **4.8. Hyperpolarized Xenon (Xe-129) MR Imaging**

Xenon (Xe) is an inert, non-toxic noble gas. Atmospheric air contains approximately 0.04 mol% of xenon. The xenon isotope Xe-129 is employed for hyperpolarized xenon MR imaging. The natural abundance of Xe-129 in atmospheric Xe is 26%, and can be extracted relatively easily.

Previous applications of xenon include use as an anaesthetic at high concentrations (at > 3 times the concentration to be used in this study and with ongoing delivery rather than a single breath), in scintigraphic and CT brain perfusion studies and as an inhaled contrast agent in CT (56, 57). Xe-129 is ten times more soluble than He-3 in water and one hundred times more soluble in lipid-rich tissue. Xenon's vastly increased solubility in blood and lipid-rich tissue demonstrates a partition coefficient of approx 0.1 (58). This property of Xe-129 may be exploited to evaluate gas exchange between alveoli and capillaries, and to provide information regarding the diffusion capacity (18, 59-65). In addition to assessment of ventilation and ADC in the gas spaces possible with He-3, Xe-129 allows for dissolved-phase imaging (14).

Following inhalation, approximately only 2% of Xe-129 is dissolved into the lung parenchyma or blood. The blood circulation distributes dissolved Xe-129 throughout the body enabling perfusion imaging in different organs. The MR signal characteristics of Xe-129 are strongly influenced by its environment such that the signal from dissolved-phase Xe-129 is significantly different to that of the gas-phase. A chemical shift of signal in the dissolved-phase is seen of approximately 200 parts per million from that of the gas-phase. Chemical shifting imaging in the lungs and other body organs has been demonstrated in rat models (66, 67). Investigation of hyperpolarized Xe-129 MR signal characteristics has revealed different signals corresponding to Xe-129 compartmentalized within fat, tissue and red blood cells. Simultaneous ventilation perfusion studies of the lung are

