### **8.2. Inclusion Criteria**

- Participant is willing and able to give informed consent for participation in the trial.
- Male or Female, aged 18 years or above.
- Patients where radiotherapy or chemoradiotherapy (concurrent or sequential schedule) affecting the lung is considered appropriate by the treating clinical Oncologist.
- WHO performance status 0-2
- Able (in the Investigators opinion) and willing to comply with all study requirements.

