**Hyperpolarized Xenon gas MR Imaging in Radiotherapy**

Pulmonary function tests will be carried out, including spirometry, lung volumes and carbon monoxide transfer factor. Recordings will be compared to predicted values determined from standard published data.

Spirometry will involve the participant breathing out as fast as they can for as long as they can, at least three times. The maximal amount breathed out in one second (forced expiratory volume in one second, FEV1) and total amount breathed out (forced vital capacity, FVC) will be recorded. Recorded values will be compared to predicted values determined from standard reference tables. Spirometry may be repeated following bronchodilator or steroid therapy to assess for reversibility as indicated by improvement FEV1 if a clinical history of asthma or chronic obstructive pulmonary disease (COPD) is present.

**Analysis** will be based on change in % predicted values over time.

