**Hyperpolarized Xenon gas MR Imaging in Radiotherapy**

For the actual Xe-129 MRI scan, the patient breathes out, and then breathes in from a bag containing up to 1L of xenon, balance nitrogen. The total volume of gas participants inhale for Xe-129 MRI scans is 1L, however this may consist of a mixture of 50-100% hyperpolarized xenon and up to 50% nitrogen i.e. 500 mL to 1L of hyperpolarized xenon is mixed with medical grade nitrogen to make up a total volume of 1L. Breathing in xenon is challenging for some people because it has a density 4.55 time greater than air, which increases airways resistance (72). Therefore patients are sometimes given assistance with the respiratory manoeuvre by physically compressing the bag during inhalation. The patient receives a bag full of air or oxygen to practice this breathing manoeuvre before breathing xenon. Scanning then takes place during a breath hold for approximately 20 seconds, or during an inhalation-exhalation manoeuvre. This manoeuvre with scanning will be repeated up to four times to enable acquisition of all Xe-129 MRI sequences. The four inhalations may be different sequences or the same sequence may be repeated to assess reproducibility. There are currently three confirmed sequences (ventilation, ADC and dissolved phase) with further sequences under technical development that will be introduced during the course of the study period.

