#### Technique development

- Assessments of detailed regional data, with regional ADC and bronchial wall thickness measurements.
- Accurate co-registration of *global* and *regional* data from Xe-129 lung MRI and chest CT, by correlating lung masks obtained from CT and proton MRI scans. Analysis of the correlation of MRI ADCs with CT lung tissue density (measured in Hounsfield units).
- Development of perfusion data (blood flow through the lungs) obtained using dissolved phase Xe-129 lung MRI, and validation against the current gold standard – ventilation/perfusion nuclear medicine scanning.
- Development of novel and automated analysis methods, based on computational models of lung function and combined anatomical and functional information from CT and MRI scans, following current work at the Computational Biology Group.
- Comparison of hyperpolarized Xe-129 MR imaging and four-dimensional CT (4D-CT) at baseline.

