**12.2. The Number of Participants**

The total sample size will be 30.

It is not possible to perform a detailed power calculation regarding sample size because this is the first time regional lung hyperpolarized Xe-129 MR indices have been correlated with physiological and functional outcomes in patients considered suitable for radiotherapy affecting the lung. We have taken the number of potential participants who are referred to our Oxford centre and considered suitable for radiotherapy affecting the lung over the last year into careful consideration and are confident that this sample size is feasible.

In our development work with this technology using He-3 gas, we have shown in 24 patients with COPD that hyperpolarized gas MR imaging identifies more lung regions affected by emphysema (defined from ADC values  $>0.34 \text{ cm}^2/\text{s}$ ) than does the severity of emphysema quantified by thoracic CT (defined from lung attenuation  $<960\text{HU}$ , a standard CT index).

To date most studies employing hyperpolarized Xe-129 have been on animal models and healthy volunteers and have reported it as a viable functional lung imaging modality (18, 65). The sample size proposed for this trial will be sufficient to be informative in our planned analyses and direct future investigation.

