**12.3. The Level of Statistical Significance**

The level of significance will be set at  $p<0.05$ .

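### Dissolved-phase Xe-129 change and carbon monoxide transfer can both move with haemoglobin, which the readable plan neither records nor adjusts for; ventilation and ADC are not affected

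*Combined protocol and SAP*

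**What the plan says.** **Dissolved-phase imaging.** Section 9.5 states "There are currently three confirmed sequences (ventilation, ADC and dissolved phase", with others still in development. The background in section 4.8 describes "different signals corresponding to Xe-129 compartmentalized within fat, tissue and red blood cells". Section 12.1, under technique development, plans "Development of perfusion data (blood flow through the lungs) obtained using dissolved phase Xe-129 lung MRI", to be validated against the nuclear medicine ventilation/perfusion scan. Section 9.5 makes that scan optional and baseline-only.

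**Gas transfer.** For lung cancer patients, section 9.5 says "Pulmonary function tests will be carried out, including spirometry, lung volumes and carbon monoxide transfer factor". The analysis is change in percent predicted over time. Section 12.1 also uses gas transfer, with FEV1, as a comparator in the hypothesis that Xe-129 MRI correlates more closely with breathlessness.

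**Population and design.** Section 8.2 admits "Patients where radiotherapy or chemoradiotherapy (concurrent or sequential schedule) affecting the lung is considered appropriate by the treating clinical Oncologist". Section 9.4 confirms that there is no randomisation. Section 12.2 says "The total sample size will be 30" and "It is not possible to perform a detailed power calculation regarding sample size". Under section 7.1 only one of the three follow-up visits is compulsory.

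**Endpoint.** Sections 6 and 12.1 define the primary outcome as change in Xe-129 imaging from baseline and name no parameter.

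**Haemoglobin.** It appears in none of the assessment lists in sections 9.3, 9.5, 9.6, 9.8 and 9.9, and section 12 names no covariate. The half-way visit and the baseline for other diagnoses are closed lists without a blood test. The flow charts in section 7.2 are not in the text available to me.

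**The concern.** A signal that comes partly from xenon in red cells should depend on how many red cells are present as well as on how much blood flows. Carbon monoxide uptake depends on haemoglobin too; the protocol does not say so, and I take it from general physiology. If haemoglobin falls during treatment, both measures could fall with no lung injury, over the same weeks in which a radiotherapy effect is sought.

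Within-patient change is the only evidence in this design, so no comparison arm removes a systemic drift. Two results are exposed: a dissolved-phase fall read as lost perfusion, and a correlation between dissolved-phase and gas-transfer changes read as agreement about lung function when both may be following the blood count. The ventilation/perfusion scan, done only at baseline, cannot separate these explanations for later change. Without recorded haemoglobin values, neither can the planned analysis.

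**Working it through.** **The plan's own figure.** The sample size of 30 rests on feasibility. No effect size, SD or power is given, so it cannot be reproduced. A paired t-test at two-sided 0.05 (section 12.3 sets 0.05; two-sided is assumed) has 80% power for a mean change of 0.53 SD with 30 pairs and 0.78 SD with 15.

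**Assumed inputs; none is in the documents.**
- True lung change: none.
- Mean haemoglobin fall f = 10%, with SD of change h = 5% or 10%.
- Dependence of the dissolved-phase signal on haemoglobin k = 1 (full) or 0.5 (half). Half matters because no separated red-cell index is planned, and the signal also comes from tissue and fat.
- Other noise in the change, SD s = 10%, 20% or 30%. No reproducibility figure is given.
- Pairs n = 30 (maximum) or 15, because two of the three follow-up visits are optional.

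**Spurious change.** Apparent fall = k·f. SD = √(s² + (k·h)²). Noncentrality = √n · k·f / SD, with n − 1 degrees of freedom.

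- Strongest case: k = 1, s = 10, h = 5. SD = √(100 + 25) = 11.18; noncentrality = 5.477 × 10 / 11.18 = 4.90; probability 0.997.
- Weakest case: k = 0.5, s = 30, h = 10. SD = √(900 + 25) = 30.41; noncentrality = 5.477 × 5 / 30.41 = 0.90; probability 0.14.

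Probability of a significant spurious fall (h = 5% first, then 10%):

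| k | s | n = 30 | n = 15 |
|---|---|---|---|
| 1 | 10% | 0.997, 0.96 | 0.90, 0.72 |
| 1 | 20% | 0.73, 0.66 | 0.42, 0.37 |
| 1 | 30% | 0.41, 0.39 | 0.22, 0.21 |
| 0.5 | 10% | 0.73, 0.66 | 0.42, 0.37 |
| 0.5 | 20% | 0.26, 0.25 | 0.14, 0.14 |
| 0.5 | 30% | 0.14, 0.14 | 0.09, 0.09 |

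With a 5% mean fall the same formula gives 0.06 to 0.66 at n = 30.

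**Spurious correlation with gas transfer.** Let gas transfer take a fraction c = 0.5 to 1 of the haemoglobin change, with k = 1 and noise s in both measures. Then r = c·h² / √((s² + h²)(s² + c²h²)). For c = 1, s = 10, h = 10: r = 100 / √(200 × 200) = 0.50. Chance of significance by Fisher's z:

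| s | h | r | 30 pairs | 15 pairs |
|---|---|---|---|---|
| 10% | 5% | 0.11–0.20 | 9–18% | 7–11% |
| 10% | 10% | 0.32–0.50 | 40–81% | 21–48% |
| 20% | 5% | 0.03–0.06 | 5–6% | 5–6% |
| 20% | 10% | 0.11–0.20 | 9–18% | 7–11% |

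Thirty pairs is an upper limit here. Full lung function testing is confined to lung cancer patients and is not done at the half-way visit, so 30 requires an all-lung-cancer cohort with full attendance.

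**The case against.** Several points on the other side are sound.

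- **Scope.** The imaging analysis in section 9.5 names ventilation and ADC, and the cross-group comparison in section 12.1 uses ADC. Neither depends on this argument. Dissolved-phase perfusion is listed as technique development.
- **Premises.** The protocol permits chemoradiotherapy but gives no proportion receiving it and no expected haemoglobin fall. It neither states nor excludes haemoglobin correction by the lung function laboratory.
- **Other evidence.** Lung cancer patients are offered gadolinium-enhanced lung MRI at baseline, final day and 3 months, which could help expose a discrepancy. A systemic fall should also shift irradiated and spared lung together, unlike local injury. However, no such comparison is specified for dissolved-phase change, and other diagnoses do not have the gadolinium scan.
- **Superiority hypothesis.** If haemoglobin also affects breathlessness, it would raise the correlation of gas transfer with dyspnoea too, so the bias does not clearly favour Xe-129.

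A reader might infer that the primary endpoint as a whole is confounded by anaemia, or that most participants will become anaemic and a false finding is nearly certain. The documents do not support either inference. The primary endpoint is exposed only because its parameter is unnamed, which is a separate and larger gap. The near-certain figures require the smallest noise, full dependence and 30 pairs together.

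What remains is that the readable plan cannot distinguish a blood-count effect from a lung effect in these two measures.

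**Conclusion.** The concern holds in a limited form. Dissolved-phase change and, in lung cancer patients, gas-transfer change can be misread when haemoglobin moves, and the readable plan has no means of detecting it. The red-cell link follows from section 4.8; the gas-transfer link and the size of any haemoglobin fall are assumptions.

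For a 10% mean fall and no lung change, the risk of a spurious significant dissolved-phase fall runs from about 14% to 99.7% at 30 pairs and from 9% to 90% at 15. A spurious significant correlation with gas transfer occurs in about 5–81% of trials at 30 pairs and 5–48% at 15, against a nominal 5%. Ranges this wide do not establish that bias will occur. They show that it cannot be dismissed without haemoglobin data. This is a cheap improvement worth making, not a flaw that undermines the trial.

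**What to change.** - **Sections 9.5, 9.6, 9.8 and 9.9:** add a CRF field for the routine haemoglobin, with its date, nearest each Xe-129 scan and each gas-transfer test. Take it from hospital laboratory records, which section 13.1 already lists as source data. Fix in advance how many days count as nearby.
- **Sections 9.5 and 12.1:** analyse haemoglobin-corrected transfer factor. Analyse dissolved-phase change with change in haemoglobin as a covariate, beside the unadjusted result. Leave the covariate uncentred, so that the intercept is the mean change at zero haemoglobin change; if it is centred on its mean, the intercept is simply the unadjusted change.
- **Missing counts:** keep these participants in the ventilation and ADC analyses, and report dissolved-phase and gas-transfer results with and without them.

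The cost is one field taken from existing records and one covariate, with no new blood test or visit. Some visits will have no nearby count. One degree of freedom is used, and the adjusted mean is less precise: its standard error grows by about √(1 + f²/h²). With f = 10% that is √2 = 1.41 for h = 10% and √5 = 2.24 for h = 5%, before allowing for the noise that the covariate removes. The adjusted result should therefore be read as a sensitivity analysis, not as a replacement.
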